## 9.8 STATISTICAL TESTING OF EFFECTIVENESS ENDPOINTS

For co-primary endpoint 1, the test of superiority of the toric lens over the control lens to result in less residual cylinder, a Wilcoxon rank-sum test will be performed, given that the distribution of residual cylinder will be discrete and likely skewed, the t-test is used only as a preliminary estimate of the needed sample size. Given the loss of power due to the use of a non-parametric test, an assumed loss of power of 5% has been made to accommodate lower power of the Wilcoxon test. The point estimate of the difference and a 95% confidence interval of the treatment effect will be provided based on the mean difference and its standard error.

For co-primary endpoints, where axis stability is examined, the upper 95% boundary of a Clopper-Pearson confidence interval will be used to test if the null hypothesis can be rejected. Number and percentage of eyes achieving various levels of stability will be summarized.

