## 1 PROTOCOL SUMMARY

### 1.1 SYNOPSIS

[figure not shown]
Title	Clinical investigation of the safety and effectiveness of Monofocal PODEYE TORIC Intraocular Lens (IOL)
Study Description	This study is a prospective, multicenter, randomized, double masked trial comparing an investigational Monofocal Toric intraocular lens (IOL) (PODEYE TORIC CYL 1.5 D) and a commercially available non-toric monofocal IOL (Alcon AcrySof SA60AT).
Study Objective	The purpose of this clinical trial is to evaluate the safety and effectiveness of Monofocal PODEYE TORIC Intraocular Lens (IOL)
Endpoints	
Co-Primary Effectiveness Endpoints
 
[REDACTED]
 
4. [REDACTED]
 
Co-Primary Effectiveness Endpoint Targets
 

1. Statistically significant smaller residual manifest cylinder in toric arm than in control arm.

2. 90% of eyes at target.

3. 95% of eyes at target.

4. 90% of eyes at target per the ANSI Z80.30 rotation criteria.

 
Co-Primary Safety Endpoints
 

1. Cumulative rate of secondary surgical interventions (SSIs) related to the optical properties of the IOL at Form 4, including IOL rotation SSIs for misalignment.

2. Rates of cumulative and persistent AEs at Form 4 via comparison to the ISO Safety and Performance Endpoint (SPE) rates as described in ISO 11979-7.

3. BCDVA logMAR of 0.3 or better is not less than ISO 11979-7:2018 tables E.3 and E4 (toric IOL arm only) at Form 4.

Statistical Analysis and Sample Size Calculation	
Hypothesis tests for co-primary effectiveness endpoints 1 through 4 must reject their associated null hypotheses in order to claim the effectiveness of the PODEYE TORIC IOL. No multiplicity adjustment of the significance level (i.e., Type I error probability) is performed.
 
[REDACTED]
 
[REDACTED]
 
Based on individual power calculations for each co-primary endpoints 1 through 4, up to 300 eyes enrolled, with 230 eyes randomized to the two IOL groups using a randomization ratio of 1:1 is sufficient for the four hypotheses associated with co-primary endpoints to reject their respective null hypotheses.

Study Population	
The subject population will consist of subjects with cataract and pre-existing corneal astigmatism in at least one eye with no other ocular comorbidity and planned for routine cataract surgery.

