#### Co-Primary Effectiveness Endpoints

1. [REDACTED]
- [REDACTED]
- [REDACTED]
- [REDACTED]

With performance goals of:

1. Statistically significant smaller residual manifest cylinder, of 0.4D or greater, in toric arm than in control arm.
2. 90% of eyes at target
3. 95% of eyes at target
4. 90% of eyes at target

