## 6.3 MEASURES TO MINIMIZE BIAS: RANDOMIZATION AND MASKING

Subjects will be randomly assigned to receive either the investigational PODEYE TORIC CYL 1.5D IOL or the AcrySof monofocal non-toric IOL in the study eye according to the randomization schedule (1:1 ratio) provided. The randomization schedule will be computer-generated and programmed by an independent statistician who is not involved in the day-to-day conduct of the study. Randomization is to occur following the completion of informed consent and screening procedures. Randomization will be stratified by site.

To minimize bias, site personnel performing postoperative study assessments of visual performance, including manifest refraction and visual acuity, will be masked to subject treatment assignment until after the final database lock ("masked assessors"). Any unmasking of the masked assessor or any study subjects must be reported to the Sponsor. Every attempt should be made to have the same masked assessor perform the same postoperative measurements for an individual subject throughout the subject's study participation.

Subjects will also be masked to their assigned treatment group (test or control group). Any material that may indicate the subjects' assigned treatment (e.g., packaging, documents) will be removed from areas where subjects and/or masked personnel may see it. Unmasked personnel should further be instructed to avoid conversation and communication with masked personnel, subjects, and persons other than the study investigator regarding subjects' assignments, outcomes, clinical courses and all other information potentially relevant to the study and its conduct.

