### 9.4 HYPOTHESES

Formal statements for the four effectiveness hypotheses are as follows.

[REDACTED]

[REDACTED]

[REDACTED]

Page 35 of 45

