8.4.1 Co-Primary Effectiveness Endpoints

Co-Primary Effectiveness Endpoints

[REDACTED]

With performance goals of:

1. Statistically significant smaller residual manifest cylinder, of 0.4D or greater, in test arm than in control arm.
 2. 90% of eyes at target.
 3. 95% of eyes at target.
 4. 90% of eyes at target.
- [REDACTED]
- [REDACTED]
- [REDACTED]
- [REDACTED]

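### Co-primary 1: as far as the plan can be read, the primary analysis uses neither the site strata nor preoperative corneal cylinder, which costs some precision; separately, the synopsis omits the 0.4 D in the goal

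*Protocol*

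**What the plan says.** **Test and estimate.** Protocol 9.8 describes "the test of superiority of the toric lens over the control lens to result in less residual cylinder" and specifies that "a Wilcoxon rank-sum test will be performed, given that the distribution of residual cylinder will be discrete and likely skewed". It adds that "a 95% confidence interval of the treatment effect will be provided based on the mean difference and its standard error". No stratum or covariate is named for either.

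**Design.** Protocol 6.3: "Randomization will be stratified by site". The Schedule of Activities has keratometry at the preoperative visit for all subjects, and inclusion criterion 4 limits preoperative corneal astigmatism to 0.75-1.50 D.

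**Where these two factors are used.** Site enters the poolability analyses (Protocol 9.10, SAP 8.7.1). Preoperative keratometric cylinder enters descriptive tables, a regression plot and stratified summaries (Protocol 9.11, SAP 8.4.4 and 8.7.2), none of them a primary test.

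**Goal.** Protocol 3.1: "Statistically significant smaller residual manifest cylinder, of 0.4D or greater, in toric arm than in control arm". SAP 8.4.1: "Statistically significant smaller residual manifest cylinder, of 0.4D or greater, in test arm than in control arm". The synopsis (Protocol 1.1) has only "Statistically significant smaller residual manifest cylinder in toric arm than in control arm".

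**What cannot be read.** Protocol 9.4 opens with "Formal statements for the four effectiveness hypotheses are as follows" and is then redacted. The text after the goals in SAP 8.4.1 is also redacted, and SAP section 2 gives the SAP precedence over the protocol on methods.

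**The concern.** A randomization stratified by site is normally followed by an analysis that recognises site. Preoperative cylinder is the obvious baseline predictor of this outcome: the control lens has no toric correction, so a control eye that starts at 1.50 D should finish with more residual cylinder than one that starts at 0.75 D. A two-sample rank-sum test and a raw mean difference both leave that predictable spread in the error term. At stake are a wider interval and a somewhat less sensitive test than the collected data allow, on an endpoint that must succeed for the study to succeed. The error rate of the test is not at stake.

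The differing statements of the goal are a second, smaller matter. The same success criterion appears with and without 0.4 D, so a reader of the synopsis and a reader of section 3.1 would describe it differently.

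**Working it through.** **1. The plan's own figures.** Overall power: 0.94 × 0.99 × 0.99 × 0.99 = 0.912, which reproduces the stated 91%. Evaluable eyes: 230 × (1 − 0.13) = 200.1, about 100 per arm. The 0.94 for co-primary 1 cannot be reproduced, because its assumed difference and SD are not visible.

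**2. How cylinder acts in each arm.** The toric lens corrects 1.03 D at the corneal plane (Protocol Table 1). Ignoring rotation and surgical change:
- Control eyes: residual runs from 0.75 to 1.50 D, rising with preoperative cylinder.
- Toric eyes: 0.75 − 1.03 = −0.28 D and 1.50 − 1.03 = +0.47 D. The magnitude falls from 0.28 D to zero and then rises to 0.47 D.

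Cylinder is therefore prognostic mainly in control eyes, and one slope common to both arms would fit poorly.

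**3. Variance removed.** With equal arms and a separate slope in each, the proportional cut in the variance of the difference is (R²c·σ²c + R²t·σ²t) / (σ²c + σ²t), where c is control and t is toric. The documents give none of these terms, so they were simulated. Assumptions: cylinder uniform on 0.75-1.50 D, corneal-change SD 0.2-0.4 D, rotation SD 5 degrees.
- One set of runs gave adjusted-to-unadjusted variance ratios of 0.93, 0.87 and 0.79, that is, cuts of 7%, 13% and 21%.
- A separate set, with 200 eyes, gave cuts of 9-27%.
- The mean rank statistic rose by 9-33% in the first set and 4-15% in the second. The spread shows how far the gain depends on the inputs.

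**4. What this means for power.** Assume a true difference of 0.4 D, 100 eyes per arm and two-sided 0.05. The SD that gives power 0.94 is 0.4 × √50 / (1.960 + 1.555) = 0.805 D. If 0.94 was reached by taking the 5% rank-test allowance off 0.99, it is 0.4 × √50 / (1.960 + 2.326) = 0.66 D. With a share R² of variance removed, power = Φ(0.4 × √50 / (SD × √(1 − R²)) − 1.960):

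| R² | Effective N, 1/(1 − R²) | Power, SD 0.805 | Power, SD 0.66 |
|---|---|---|---|
| 0 | 1.00 | 94.0% | 99.0% |
| 0.05 | 1.05 | 95.0% | 99.3% |
| 0.10 | 1.11 | 95.9% | 99.5% |
| 0.20 | 1.25 | 97.5% | 99.8% |
| 0.30 | 1.43 | 98.7% | 99.9% |
| 0.40 | 1.67 | 99.5% | 99.98% |

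The gain is 0 to about 6 points over the whole table. For a variance cut of 7-27% it lies between the rows for 0.05 and 0.30: about 1 to 5 points at SD 0.805, and under 1 point at SD 0.66.

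**5. The rank test itself.** A simulation used 10 sites of 20 eyes, outcomes in 0.25 D steps and 400 runs per cell (Monte Carlo standard error at most √(0.25/400) = 2.5 points). It compared the plain rank-sum test with a rank ANCOVA on site and cylinder:

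| Nominal shift | Setting | Rank-sum | Rank ANCOVA |
|---|---|---|---|
| 0.2 D | Prognostic, control SD about 0.49 | 75% | 85% |
| 0.2 D | Prognostic, control SD about 0.65 | 43% | 51% |
| 0.2 D | Not prognostic, same two SDs | 73%, 48% | 73%, 48% |
| 0.4 D | All settings | at least 97% | at least 97% |

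The prognostic settings gave both arms the same cylinder slope, which by step 2 favours the adjusted test.

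**The case against.** The case for leaving the test alone is respectable. An unstratified rank-sum test after site-stratified randomization is valid and, if anything, conservative. Site and cylinder are examined elsewhere in the plan. Power at 0.4 D is already high, so adjustment buys a few points at most, and every figure for the gain rests on assumed inputs. The redacted SAP text governs and may already contain an adjusted analysis. A rank ANCOVA beside an adjusted mean difference still pairs a test on ranks with an estimate in dioptres, so the two can still disagree.

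All of this stands as a limit on the size of the point. It does not explain why a strong baseline predictor, already collected, should be left out of the primary comparison and its interval. Examining a factor in a supportive table does not sharpen the primary estimate.

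A reader might also infer something stronger: that the test is against no difference, that the 0.4 D goal is never tested, and that a benefit well short of it would count as success. The documents do not support this. The formal null and the matching SAP text are redacted, and could hold a 0.4 D null, a shifted rank test or a rule on the estimate. Protocol 3.1 and SAP 8.4.1 put 0.4 D in the performance goal itself, and Protocol 9.6 and SAP 8.1 require every co-primary endpoint to be met. Read together, they can already require 0.4 D. Adding a rule that the observed difference must reach 0.40 D would not be cheap either: if the truth is 0.40 D, a symmetric estimate passes only about half the time.

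**Conclusion.** The point holds as a modest loss of precision in a valid analysis. On the readable text, neither the primary test nor the reported difference for co-primary 1 uses site or preoperative keratometric cylinder. Adjustment would cut the variance of the difference by roughly 7-27% if cylinder is spread evenly over 0.75-1.50 D with the corneal-change and rotation SDs assumed above. It would gain little or nothing if the factors are not prognostic. At an assumed 0.4 D difference the gain is about 0-6 power points, so the main benefit is a tighter interval, and some protection if the true difference is smaller than planned.

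The omission of 0.4 D from the synopsis is a plain inconsistency between visible passages. No conclusion is drawn about whether the hidden hypothesis tests 0.4 D.

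**What to change.** Before unmasking, in Protocol 9.8 and the matching SAP section:

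- Make the primary test of co-primary 1 a rank-based ANCOVA on arm, preoperative keratometric cylinder and site. A site-stratified van Elteren test is the minimum; it uses site but not cylinder.
- Report a mean difference and 95% interval adjusted for the same factors. Allow a cylinder-by-arm slope because the toric correction is a fixed 1.03 D, and centre cylinder at its overall mean so that the arm term is the average difference.
- Pool over the 50 imputations. The imputation predictors visible in SAP 8.4.3 are attempted toric correction, age and sex; cylinder and site should be among them once the analysis uses them.
- State in advance how very small sites are combined, so that no eye leaves the primary analysis.
- Keep the plain Wilcoxon test and raw mean difference as sensitivity analyses.

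Separately, align the synopsis with Protocol 3.1 and SAP 8.4.1 on the 0.4 D wording, and check all three against the redacted hypothesis. No new 0.4 D decision rule is proposed.

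The cost is wording, slightly more modelling and programming, and about nine degrees of freedom for ten sites out of roughly 200 eyes. No new data are needed.

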## 9.9 STATISTICAL TESTING OF SAFETY ENDPOINTS

Cumulative and persistent adverse events from ISO 11979-7 (2018) Table E.2 will be summarized using descriptive statistics by AE type and treatment and will be compared to the maximum number of cases allowed before the ISO SPE rate is exceeded. Summaries will be provided for both spherical and toric lenses.

The other safety outcomes, listed in Section 3.1, will be summarized by count and percentage for each IOL type. Adverse events will be tabulated by type (e.g., all, serious, anticipated, unanticipated) and classification by IOL.

[REDACTED]

#### 9.10 POOLABILITY

Poolability of results will be assessed by site. The binary co-primary effectiveness endpoints addressing performance of the toric IOL will be tabulated by site to determine if success rates indicate a difference in effectiveness. Similarly, the degree of superiority of the toric arm in reducing residual cylinder, compared with the control arm, will be tested. Cross-tabulations of site by binary endpoints will be analyzed with a Fisher's exact test and the comparison of residual cylinder between treatment arms will be analyzed with an analysis of variance model with an interaction term for site by treatment. In both cases, a p-value of 0.15 will indicate that potential site differences exist and will require investigation as to the possible causes.

#### 9.11 ADDITIONAL ENDPOINTS AND ASSOCIATED ANALYSES

The following are not subject to hypothesis testing.

- 1) Achievement of  $\leq 0.50$  D reduction in cylindrical power of the eye as a binary endpoint. Analysis will summarize the overall percentage of eyes meeting endpoint 1 as well as by each 0.25 D step of preoperative keratometric cylinder. Tabulation will be by both arms at Form 4.
- 2) Reduction in cylindrical power of the eye at Form 4. Analysis will include summary statistics of reduction in cylinder power of the eye overall and by each 0.25 D step of preoperative keratometric cylinder. Summary statistics will be provided for both treatment arms, with the addition of a 95% confidence interval of the mean for each arm. Number and percentage with an absolute reduction of  $\leq 0.5$  D will be provided for each arm.
- 3) Relationship between reduction in cylindrical power of the eye at the corneal plane and preoperative keratometric cylinder at Form 4. The association will be shown using a scatterplot with a linear regression line for each treatment arm. Intercept and slope, with associated p-values, will be provided. If the scatter of the data do not appear to be linear, a LOESS curve will be added for each arm.
- 4) The surgically induced change in corneal cylinder is calculated by analysis of the preoperative and postoperative keratometric readings (power and axis of meridians of highest and lowest power), converted to components in dioptric space. Change is defined as postoperative component values minus preoperative component values. Change and percentage change from baseline at Form 4 will be summarized with descriptive statistics for each treatment arm, overall, and by preoperative keratometric cylinder categories. Analyses will include:
  - a) Analysis of the error in the predicted magnitude of postoperative astigmatism, including the bias, standard deviation, and mean absolute error, and a similar analysis of error in the predicted axis;

- b) Bar plot of the absolute error in predicted keratometric axis as a function of preoperative corneal astigmatism, and tabulation of the proportion of eyes with absolute error in axis by 5° wide bins (e.g., 0° to 5°, >5° to 10°).
- 5) Achievement of UCDVA of 0.0 logMAR or better, 0.2 logMAR or better, and of 0.3 logMAR or better at Form 4. Results will be tabulated for each treatment arm by N and percentage.
- 6) UCDVA at Form 4. UCDVA will be summarized with summary statistics, overall and by each 0.25 D step of preoperative keratometric cylinder categories. Both treatment arms will be summarized.
- 7) Manifest cylinder at Form 4. Analysis will include summary statistics of manifest cylinder. Summary statistics will be provided for both treatment arms. Results will be summarized overall as well as stratified by each 0.25 D of preoperative keratometric cylinder.
- 8) Achieving accuracy of cylinder to target at Form 4 within 0.25 D, 0.50 D, and 0.75 D. Results will be tabulated for each treatment arm by N and percentage.
- 9) Achieving accuracy of MRSE to target at Form 4 within 0.25 D, 0.50 D, and 0.75 D. Results will be tabulated for each treatment arm by N and percentage.
- 10) Axis misalignment compared to target within specified accuracy at Form 4. Results will be tabulated for the toric lens only, reporting the number and percentage with axis deviation greater than 30° of target.
- 11) Axis misalignment at Form 4. Results for absolute and signed values will be summarized for the toric lens only, with summary statistics of deviation from target. A two-sided tolerance interval around the mean of the signed value, which contains at least 90% of the population (with 95% probability), will be provided.

## 10 SUPPORTING DOCUMENTATION AND OPERATIONAL CONSIDERATIONS

### 10.1 REGULATORY, ETHICAL, AND STUDY OVERSIGHT CONSIDERATIONS

#### 10.1.1 INFORMED CONSENT PROCESS

##### 10.1.1.1 CONSENT/ASSENT AND OTHER INFORMATIONAL DOCUMENTS PROVIDED TO PARTICIPANTS

The study ICF has been developed in compliance with 21 CFR Part 50.25. Study ICFs and any other subject-facing materials (e.g., recruitment materials, subject instruction sheets) must be submitted to and approved by the IRB prior to implementation. Any IRB-requested modifications to the consent form must remain in compliance with 21 CFR Part 50.25. Each participant must be provided with a copy of the IRB-approved ICF for their review, and the participants' written approval must be provided prior to initiation of study procedures.

##### 10.1.1.2 CONSENT PROCEDURES AND DOCUMENTATION

The investigator or designee will explain the study purpose, procedures and responsibilities to the potential participant and provide sufficient opportunity to ask questions, while allowing adequate time for

consideration of the information provided. Documentation of written consent for study participation must be present prior to initiation of any study-specific procedure, and subjects will be considered enrolled in the study upon their signature on the ICF.

---

#### 10.1.2 STUDY DISCONTINUATION AND CLOSURE

The Sponsor reserves the right to terminate the study at any time. If the clinical study is prematurely terminated or suspended, the Sponsor will inform the Investigators and the regulatory authorities of the reason for the termination/suspension. The Investigator should promptly notify the IRB of the termination or suspension and of the reasons. If the Sponsor terminates the study for safety reasons, it will promptly notify the Investigators and provide written instruction for study termination and applicable subject follow-up.

Circumstances that may warrant termination or suspension include, but are not limited to:

- Determination of unexpected, significant, or unacceptable risk to participants
- Demonstration of insufficient effectiveness that would warrant stopping
- Insufficient compliance to protocol requirements
- Data that are not sufficiently complete and/or evaluable
- Determination of futility

If the study is suspended, it may resume once concerns about safety, protocol compliance, and data quality are addressed, and satisfy the Sponsor, IRB and/or Food and Drug Administration (FDA).

If, in the opinion of the investigator, the clinical observations in the study suggest that it may be unwise to continue, the investigator may terminate the study at his or her site after consultation with the Sponsor. A written statement fully documenting the reasons for such a termination will be provided to the Sponsor.

---

#### 10.1.3 CONFIDENTIALITY AND PRIVACY

The investigator will maintain the confidentiality of the identity of subjects enrolled in the study and the information contained in the study records. The records will be made available as required for review by the FDA and other governing regulatory authorities, as well as reviewing IRBs; however, to the extent possible, the subject's identity will not be disclosed.

---

#### 10.1.4 DOCUMENT RETENTION

Source documents may include a subject's medical records, hospital charts, clinic charts, the investigator's study subject files, as well as the results of diagnostic tests such as X-rays, laboratory tests, and electrocardiograms. The investigator's copy of the Case Report Forms serves as the investigator's record of a subject's study-related data.

All study related correspondence, patient records, consent forms, record of the use of the study device and copies of case report forms will be maintained on file for at least two years after the last approval of a marketing application and until there are no pending or contemplated marketing applications; or until at least two years have elapsed since the formal discontinuation of clinical development of the investigational device. These documents will be retained for a longer period if required by the applicable

regulatory requirements or by an agreement with the Sponsor. It is the responsibility of the Sponsor to inform the investigator/institution as to when these documents no longer need to be retained or should be forwarded to the Sponsor.

If the responsible investigator retires, relocates, or for other reasons withdraws from the responsibility of keeping study records, custody must be transferred to a person who will accept the responsibility. The Sponsor must be notified in writing of the name and address of the new custodian.

---

